5.7 Study Drug

[figure not shown]
All subjects will receive OnabotA X or Placebo prepared at the investigational site [REDACTED] administered on Day 1 (Baseline).

5.8 Randomization/Drug Assignment

All subjects will be assigned a unique identification number by the IRT at the screening visit. For subjects who rescreen, the screening number assigned by the IRT at the initial screening visit should be used. The IRT will assign a randomization number that will encode the subject's treatment group assignment according to the randomization schedule.

Randomization will be stratified by baseline investigator-rated AGLSS at maximum contraction, using central by block stratified randomization. The same block will not be shared across investigative sites or by baseline GL severity assessment.

Study drug will be labeled with kit numbers in an open-label fashion. The IRT will provide the IDR with the specific kit number for each randomized subject at the time of randomization (Day 1). The IDR will dispense study drug according to the IRT. The IDR will receive the IRT confirmation notifications for each transaction and will maintain these with the other unblinded study source documents with restricted access to the blinded site staff.

[REDACTED] The IDR will then provide the filled syringes to the blinded investigator, who will inject the subject according to the study treatment administration instructions in the Operations Manual ([Appendix F](#)), Section 3.15.

5.9 Protocol Deviations

AbbVie does not allow intentional/prospective deviations from the protocol except when necessary to eliminate an immediate hazard to study subjects. The investigator is responsible for complying with all protocol requirements, written instructions, and applicable laws regarding protocol deviations. If a protocol deviation occurs (or is identified, including those that may be due to the COVID-19 pandemic), the investigator is responsible for notifying independent ethics committee (IEC)/independent review board (IRB), regulatory authorities (as applicable), and AbbVie.

5.10 Data Monitoring Committee

[REDACTED] Study sites and subjects will remain blinded for the duration of the study.

The details of the interim analyses are included in Section [7.6](#).

6 SAFETY CONSIDERATIONS

6.1 Complaints and Adverse Events

Complaints

A complaint is any written, electronic, or oral communication that alleges deficiencies related to the physical characteristics, identity, quality, purity, potency, durability, reliability, safety, effectiveness, or performance of a product/device. Complaints associated with any component of this investigational product must be reported to AbbVie.

Product Complaint

A product complaint is any complaint related to the biologic or drug component of the product or to the medical device component(s).

[figure not shown]
For a product this may include, but is not limited to, damaged/broken product or packaging, product appearance whose color/markings do not match the labeling, labeling discrepancies/inadequacies in the labeling/instructions (e.g., printing illegible), missing components/product, device damage or not working properly, or packaging issues.

Medical Complaints/Adverse Events and Serious Adverse Events: OnabotA X

An AE is defined as any untoward medical occurrence in a subject or clinical investigation subject administered a pharmaceutical product and which does not necessarily have a causal relationship with this treatment. An AE can therefore be any unfavorable and unintended sign (including an abnormal laboratory finding), symptom, or disease temporally associated with the use of a medicinal (investigational) product, whether or not the event is considered causally related to the use of the product.

Such an event can result from use of the drug as stipulated in the protocol or labeling, as well as from "special situations" such as accidental or intentional overdose, medication error, occupational or accidental exposure, off-label use, drug abuse, drug misuse, or drug withdrawal, all which must be reported whether associated with an AE or not. Any worsening of a pre-existing condition or illness is considered an AE. Worsening in severity of a reported AE should be reported as a new AE. Laboratory abnormalities and changes in vital signs are considered to be AEs only if they result in discontinuation from the study, necessitate therapeutic medical intervention, and/or if the investigator considers them to be AEs.

An elective surgery/procedure scheduled to occur during a study will not be considered an AE if the surgery/procedure is being performed for a pre-existing condition and/or the surgery/procedure has

been pre-planned prior to study entry. However, if the pre-existing condition deteriorates unexpectedly during the study (e.g., surgery performed earlier than planned), then the deterioration of the condition for which the elective surgery/procedure is being done will be considered an AE.

If an AE, whether associated with study drug or not, meets any of the following criteria, it is to be reported to AbbVie clinical pharmacovigilance or Clinical Research Organization (as appropriate) as a SAE within 24 hours of the site being made aware of the SAE (refer to Section 4.2 of the Operations Manual [[Appendix F](#)] for reporting details and contact information):

Death of Subject	An event that results in the death of a subject.
Life-Threatening	An event that, in the opinion of the investigator, would have resulted in immediate fatality if medical intervention had not been taken. This does not include an event that would have been fatal if it had occurred in a more severe form.
Hospitalization or Prolongation of Hospitalization	An event that results in an admission to the hospital for any length of time or prolongs the subject's hospital stay. This does not include an emergency room visit or admission to an outpatient facility.
Congenital Anomaly	An anomaly detected at or after birth, or any anomaly that results in fetal loss.
Persistent or Significant Disability/Incapacity	An event that results in a condition that substantially interferes with the activities of daily living of a study subject. Disability is not intended to include experiences of relatively minor medical significance such as headache, nausea, vomiting, diarrhea, influenza, and accidental trauma (e.g., sprained ankle).
Important Medical Event Requiring Medical or Surgical Intervention to Prevent Serious Outcome	An important medical event that may not be immediately life-threatening or result in death or hospitalization, but based on medical judgment, may jeopardize the subject and may require medical or surgical intervention to prevent any of the outcomes listed above (i.e., death of subject, life threatening, hospitalization, prolongation of hospitalization, congenital anomaly, or persistent or significant disability/incapacity). Additionally, any elective or spontaneous abortion or stillbirth is considered an important medical event along with any suspected transmission of an infectious agent via a medicinal product if no other serious criterion is applicable. Examples of such events include allergic bronchospasm requiring intensive treatment in an emergency room or at home, blood dyscrasias or convulsions that do not result in inpatient hospitalization, or the development of drug dependency or drug abuse.

All AEs reported from the time of study drug administration will be collected for at least 30 days or until the last follow-up visit, whichever is longer, whether solicited or spontaneously reported by the subject.

In addition, study procedure-related serious and nonserious AEs will be collected from the time the subject signs the study-specific informed consent.

AbbVie will be responsible for SUSAR reporting for the IMP in accordance with global and local requirements.

Possible Distant Spread of Toxin

Possible distant spread of toxin (PDSOT) is defined as a possible pharmacologic effect of botulinum toxin at sites noncontiguous and distant from the site of injection. Utilizing a standardized methodology to assess for PDSOT, Medical Dictionary for Regulatory Activities (MedDRA) preferred terms (PTs) that may be associated with botulinum toxin effects have been prospectively identified (see the statistical analysis plan [SAP] for a complete list of these PTs). AEs reporting any of these terms will be medically reviewed on a regular basis throughout the study and will be summarized in the clinical study report.

Adverse Event Severity and Relationship to Study Drug

The investigators will rate the severity of each AE as mild, moderate, or severe.

The investigator will use the following definitions to rate the severity of each AE:

Mild	The AE is transient and easily tolerated by the subject.
Moderate	The AE causes the subject discomfort and interrupts the subject's usual activities.
Severe	The AE causes considerable interference with the subject's usual activities and may be incapacitating or life threatening.

Pregnancy

[figure not shown]
While not an AE, pregnancy in a study subject must be reported to AbbVie within 24 hours after the site becomes aware of the pregnancy. Subjects who become pregnant during the study will be encouraged to remain in the study for safety follow-up. If a pregnancy occurs in a study subject, information regarding the pregnancy and the outcome will be collected.

7 STATISTICAL METHODS & DETERMINATION OF SAMPLE SIZE

[figure not shown]
7.1 Statistical and Analytical Plans

The statistical methods provided in this protocol will be focused on primary and key secondary analyses. Complete and specific details of the statistical analysis will be described in the SAP.

7.2 Definition for Analysis Populations

The Intent to Treat (ITT) Population includes all randomized subjects. The ITT Population will be used for all efficacy analyses.

The Safety Analysis Set consists of all subjects who received at least 1 dose of study drug. The safety analyses will be based on the safety population.

7.3 Handling Potential Intercurrent Events for the Primary and Key Secondary Endpoints

Missing data will be imputed using multiple imputation (MI) method for the primary and secondary endpoints (see Section 3.2).

After imputation, the changes from baseline values will be calculated. The responder status based on raw values or change from baseline values will then be derived for each post baseline visit.

Each of the 5 imputation data sets will be analyzed individually.

To obtain pooled CMH p-value, the Wilson-Hilferty transformation will be used.

A sensitivity analysis will also be performed for the primary efficacy variable using observed data.

7.4 Statistical Analyses for Efficacy

Summary and Analysis of the Primary Endpoint

Analysis of the primary endpoint will be conducted on the ITT population based on treatment as randomized. Missing data will be imputed using MI method described in Section 7.3. The evaluation of the equality of the proportions of responders will be based on Cochran-Mantel-Haenszel (CMH) test stratified by baseline investigator-rated AGLSS at maximum contraction. Wald confidence intervals for proportions of responders and difference in the proportion of responders will be presented.

The Breslow-Day homogeneity of the odds-ratio test will be performed to test the treatment-by-investigator-rated baseline GL severity at maximum contraction interaction.

Summary and Analysis of Secondary Endpoints

The proportion of responders will be analyzed using CMH test, stratified by baseline investigator-rated AGLSS at maximum contraction. Missing data will be imputed using MI method.

Statistical testing will only be done between each OnabotA X group and the placebo group.

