3.3 Secondary Endpoints

Secondary Endpoints

- Achievement of None or Mild on the investigator-rated AGLSS assessments at maximum contraction at Day 30
- Responses of Very satisfied or Mostly satisfied on satisfaction with treatment per the FLSQ follow-up version Item 5 at Day 60
- Achievement of ≥ 14 -point psychosocial impact improvement from baseline at Day 30 per the FLSQ Impact domain, among subjects with baseline scores ≥ 14 points

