7.1 Demographics and Baseline Characteristics

Continuous demographic variables include age. Categorical demographic variables include sex, ethnicity, race, age group [REDACTED].

Baseline characteristics include weight, height, body mass index (BMI), Fitzpatrick skin type, investigator-rated and subject-rated AGLSS severity at maximum contraction and at rest, baseline Facial Line Satisfaction Questionnaire (FLSQ[©]) impact domain score,

[REDACTED]

[REDACTED]

[REDACTED]

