9.4 Secondary Efficacy Endpoints and Analyses

9.4.1 Key Secondary Efficacy Endpoints

The key secondary endpoints, which utilize both the AGLSS and FLSQ, include:

- Achievement of None or Mild on the investigator-rated AGLSS assessments at maximum contraction at Day 30;
- Responses of Very satisfied or Mostly satisfied on satisfaction with treatment per the FLSQ follow-up version Item 5 at Day 60;
- Achievement of \geq 14-point psychosocial impact improvement from baseline at Day 30 per the FLSQ Impact domain, among subjects with baseline scores \geq 14 points

9.4.2**Main Analyses of Key Secondary Efficacy Endpoints**

The attributes of the estimands corresponding to the secondary efficacy endpoints are summarized in Table 2.

Table 2. Summary of the Estimand Attributes of the Secondary Efficacy Endpoints

Attributes of the Estimand					
Estimand Label	Treatment	Endpoint	Population	Handling of Intercurrent Events	Statistical Summary
Hypothetical estimand for secondary endpoint	OnabotA X or placebo	Achievement of None or Mild on the investigator-rated AGLSS assessments at maximum contraction at Day 30	ITT (All randomized)	Subjects who discontinue study prior to Day 30 assessments, or who do not have AGLSS assessments will be included in the analysis as a hypothetical scenario in which they had not missed the AGLSS assessments	Difference in response proportions between each active treatment group and placebo, after MI using CMH test stratified by baseline investigator-rated AGLSS at maximum contraction
		Responses of Very satisfied or Mostly satisfied on satisfaction with treatment per the FLSQ follow-up version Item 5 at Day 60		Subjects who discontinue study prior to Day 60 assessments, or who do not have FLSQ assessments will be included in the analysis as a hypothetical scenario in which they had not missed the FLSQ assessments	
		Achievement of ≥ 14 -point psychosocial impact improvement from baseline at Day 30 per the FLSQ Impact domain, among subjects with baseline scores ≥ 14 points		Subjects who discontinue study prior to Day 30 assessments, or who do not have FLSQ assessments will be included in the analysis as a hypothetical scenario in which they had not missed the FLSQ assessments	

AGLSS = Allergan Glabellar Line Severity Scale; CMH = Cochran-Mantel-Haenszel; ITT = intent-to-treat; MI = multiple imputation; OnabotA X = onabotulinumtoxinA X

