The key secondary efficacy endpoints are to be analyzed similarly to the primary endpoint using multiple imputation, as specified in Section 9.2. [REDACTED]

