9.4.3 Sensitivity and Supplementary Analyses for Key Secondary Efficacy Endpoints

Not applicable.

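### The FLSQ Impact responder analysis does not use the baseline Impact score: the test is valid, but it gives up some precision and some protection against chance imbalance

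*Protocol*

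**What the plan says.** Protocol 3.3 and SAP 9.4.1 define the endpoint as a gain of at least 14 points in "psychosocial impact improvement from baseline at Day 30 per the FLSQ Impact domain, among subjects with baseline scores ≥ 14 points".

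Protocol 7.4 gives one method for all secondary endpoints: "The proportion of responders will be analyzed using CMH test, stratified by baseline investigator-rated AGLSS at maximum contraction". In SAP Table 2 a single statistical summary serves all three key secondary endpoints: a difference in response proportions "after MI using CMH test stratified by baseline investigator-rated AGLSS at maximum contraction". The text below the table adds: "The key secondary efficacy endpoints are to be analyzed similarly to the primary endpoint using multiple imputation, as specified in Section 9.2".

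SAP 7.1 lists the "baseline Facial Line Satisfaction Questionnaire (FLSQ[©]) impact domain score" among the baseline characteristics, so the score is available. Protocol 5.8 and SAP 2.3 stratify randomisation by site and baseline AGLSS only. SAP 9.4.3, which would hold sensitivity and supplementary analyses for the key secondary endpoints, is marked as not applicable.

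**The concern.** AGLSS is the natural stratifier for the two endpoints measured on the AGLSS. For the Impact endpoint, the variable from which change is measured is the Impact score, and the analysis ignores it apart from the entry threshold of 14.

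That score is plausibly prognostic. If the scale has its floor at 0 (an assumption, since the documents give no range), a subject who starts at 14 must improve by 14/14 = 100% to respond. One who starts at 80 needs 14/80 = 17.5%. Restricting to 14 or more removes subjects who could not respond, but leaves any gradient above the threshold.

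The endpoint is tested within the gated hierarchy of SAP 13.0. It is also analysed at each interim (SAP 12.0), and the interim data feed the Phase 3 dose recommendation (SAP 12.1). A covariate added after an imbalance has been seen would carry little weight, so the choice has to be made in advance.

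**Working it through.** **The plan's own figure.** The documents show no power, response rate or SD for this endpoint. The 28 and 14 subjects in Protocol 7.8 concern the primary endpoint and rest on redacted rates, so there is nothing to reproduce here.

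**Group sizes.** 280 subjects at 2:2:2:1 (Protocol 4.1) give 280/7 = 40 on placebo and 80 per dose group. The share with baseline Impact of 14 or more is unknown, so I take 100%, 70% and 50%.

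**Chance imbalance.** The SD of the standardised baseline difference is √(1/n₁ + 1/n₀). The probability of a difference beyond 0.3 SD comes from the normal distribution.

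| Share eligible | Dose v placebo | SD of difference | P(beyond 0.3 SD) |
|---|---|---|---|
| 100% | 80 v 40 | 0.194 | 12% |
| 70% | 56 v 28 | 0.231 | 20% |
| 50% | 40 v 20 | 0.274 | 27% |

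The three dose comparisons share one placebo group. Their correlation is (1/40)/(1/40 + 1/80) = 2/3, so an unlucky placebo draw tends to move all three the same way.

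**Effect of an imbalance.** Let R² be the within-group share of responder variance explained by the baseline score. The unadjusted risk difference then shifts by about d × √R² × √(p(1 − p)). With d = 0.3 and an assumed p = 0.35, √(0.35 × 0.65) = 0.477, and the shift is:
- R² = 0.01: 1.4 points
- R² = 0.04: 2.9 points
- R² = 0.10: 4.5 points
- R² = 0.20: 6.4 points

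**Power by formula.** Assume 56 v 28 subjects and response of 50% v 20%. The pooled rate is (56 × 0.5 + 28 × 0.2)/84 = 0.40. The null SE is √(0.24 × (1/56 + 1/28)) = 0.1134 and the alternative SE is √(0.25/56 + 0.16/28) = 0.1009. Then z = (0.30 − 1.96 × 0.1134)/0.1009 = 0.77, which is 78.0% power. Adjustment multiplies the effective sample size by 1/(1 − R²). Power becomes 78.8% (R² = 0.02), 80.2% (0.05), 82.4% (0.10) and 86.9% (0.20).

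**First simulation.** 56 v 28 subjects, about 57–58% v 27–33% responding, 6,000 trials per row. The planned CMH test is compared with a linear model containing AGLSS and the continuous baseline score, with robust (HC3) standard errors. The variance factor is adjusted over planned. Rows differ in placebo rate, so compare within rows.

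| R² | Power, planned | Power, adjusted | Variance factor |
|---|---|---|---|
| about 0.01 | 74.2% | 74.4% | 1/0.985 = 1.02 |
| about 0.04 | 71.4% | 72.6% | 1/1.009 = 0.99 |
| about 0.11 | 67.2% | 71.4% | 1/1.088 = 0.92 |
| about 0.20 | 59.4% | 68.0% | 1/1.199 = 0.83 |

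The first row is what chance alone gives in 84 subjects (1/84 = 0.012). With no treatment effect, the planned test rejected in 4.4% to 5.5% of trials.

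**Second simulation.** Baseline uniform on 14–90, 64 v 32 or 40 v 20 subjects, and improvement either proportional to baseline or unrelated to it. Across eight settings:
- Logistic regression with the continuous score and a standardised risk difference gave variance factors of about 0.81 to 1.01 and about 2 to 5 points more power.
- Its large-sample standard errors gave a type I error of about 6%.
- Part of the apparent power gain therefore comes from a slightly liberal test. Where the variance factor is near 1, none of the gain is precision.

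**The case against.** The strongest reply is that nothing is wrong with the planned test. It is stratified by the clinical factor used in randomisation, and chance imbalance in any other variable is already part of the sampling variance behind its p-value and interval. That stands. A reader might infer that the analysis is biased or that its error rate is inflated; neither the documents nor the simulations support that.

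A reader might also infer that baseline Impact is the dominant predictor of response. The documents give no FLSQ range, SD, baseline distribution or responder rate, so that is an assumption. If improvement in points is unrelated to baseline, there is nothing to gain.

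Redaction is a fair caution. Text is blacked out after the analysis sentence in SAP 9.4.2, in the imputation details of SAP 9.2, and in SAP 9.1 and 9.5. An adjusted analysis could sit there, so one cannot say that none is planned anywhere. But the visible main analysis in Table 2 names AGLSS alone. A baseline term in the imputation model would not adjust outcomes that were observed.

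The objection also rules out one obvious remedy, adding tertiles of baseline Impact to the CMH strata. That makes six strata for perhaps 32 placebo subjects, and some become very sparse. Over the same eight settings its variance factor ran from 0.86 to 1.07, so it can lose precision. Tertile cut points could also differ between interim looks unless fixed.

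**Conclusion.** The omission is plain in both documents, and its consequence is limited: lost efficiency and exposure to chance imbalance in one key secondary endpoint of a Phase 2 trial. The primary endpoint and the validity of the planned test are untouched.

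The size depends on how prognostic the baseline score is. The gain is essentially nil at R² near 0.01, a few power points near 0.10, and about 9 points (59.4% to 68.0%) at 0.20 in the first simulation. The second simulation gives about 2 to 5 points, the low end of which should be read as no gain once the type I error is held at 5%. All of these figures rest on assumed response rates, subset sizes and baseline distributions.

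The change is worth making because the score is already collected, the likely loss is about 1% to 2% in variance, and the choice cannot credibly be made after unblinding.

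**What to change.** In SAP 9.4.2 and Table 2, and in Protocol 7.4, prespecify for this endpoint:
- logistic regression with treatment, baseline investigator-rated AGLSS and the continuous baseline FLSQ Impact score, in subjects with baseline of 14 or more;
- a standardised risk difference for each dose group against placebo, so that the target remains a difference in response proportions;
- a robust standard error with a small-sample correction, combined over the five imputations by Rubin's rules;
- the same model at each interim and at the final analysis.

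State whether this is the main analysis or, at minimum, a supplementary one beside the CMH test. If main, the endpoint needs its own statistical summary in Table 2. If supplementary, SAP 9.4.3 should list it. Do not add tertile strata to the CMH test.

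The cost is wording and programming, with no new data. The downsides are about 1% to 2% in variance if the score is not prognostic, a type I error near 6% if the small-sample correction is left out, and a pooling method for this endpoint that differs from the Wilson-Hilferty approach used elsewhere.
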